#### **Adverse Events of Special Interest**

Below is a list of adverse events of special interest. Related supplemental eCRFs, if applicable, should be filled out in response to an event.

- Serious infections and opportunistic infections
- Active TB (TB screening eCRF in all subjects and supplemental TB eCRF as appropriate)
- Malignancies (all types) (Malignancy eCRF);
- Hepatic events (Hepatic AE eCRF):
  - Discontinuation or interruption of study drug due to a hepatic-related AE;
  - A hepatic-related SAE;
  - ALT/AST > 8 × ULN or ALT/AST > 3 × ULN with a total bilirubin > 2 × ULN;
- Hematologic disorders;
- Hypersensitivity reactions (Hypersensitivity Reaction Signs and Symptom eCRF).

## Adverse Event Severity and Relationship to Study Drug

The investigators will rate AEs according to the National Cancer Institute Common Terminology Criteria for Adverse Events (CTCAE) v4.0, which can be accessed at:

[https://www.eortc.be/services/doc/ctc/CTCAE\\_4.03\\_2010-06-14\\_QuickReference\\_5x7.pdf](https://www.eortc.be/services/doc/ctc/CTCAE_4.03_2010-06-14_QuickReference_5x7.pdf).

For AEs not captured by the CTCAE, the following should be used:

Grade 1	The adverse event is transient and easily tolerated by the subject (mild).
Grade 2	The adverse event causes the subject discomfort and interrupts the subject's usual activities (moderate).
Grade 3/4	The adverse event causes considerable interference with the subject's usual activities and may be incapacitating or life-threatening (severe).
Grade 5	The adverse event resulted in death of the subject (severe).

The investigator will use the following definitions to assess the relationship of the adverse event to the use of study drug:

Reasonable Possibility	After consideration of factors including timing of the event, biologic plausibility, clinical judgment, and potential alternative causes, there is sufficient evidence (information) to suggest a causal relationship.
No Reasonable Possibility	After consideration of factors including timing of the event, biologic plausibility, clinical judgment, and potential alternative causes, there is insufficient evidence (information) to suggest a causal relationship.

## Pregnancy

While not an adverse event, pregnancy in a study subject must be reported to AbbVie within 1 working day after the site becomes aware of the pregnancy. Subjects who become pregnant during the study must be discontinued (Section 5.5). If a pregnancy occurs in a study subject or in the partner of a study subject, information regarding the pregnancy and the outcome will be collected.

In the event of pregnancy occurring in a subject's partner during the study, written informed consent from the partner must be obtained prior to collection of any such information. AbbVie will provide a separate consent form for this purpose. Pregnancy in a subject's partners will be collected from the date of the first dose through 84 days following the last dose of study drug.

The pregnancy outcome of an elective or spontaneous abortion, stillbirth or congenital anomaly is considered a SAE and must be reported to AbbVie within 24 hours after the site becomes aware of the event.

## 6.2 Toxicity Management

---

The management of specific AEs and laboratory parameters is described in [Table 2](#).

The toxicity management of AEs including AEs of special interest consists of safety monitoring (review of AEs on an ongoing basis, and periodical/ad hoc review of safety issues by a DMC), interruption of study drug dosing with appropriate clinical management if applicable, and discontinuation of the subjects from study drug. There are no time limits for study drug interruption as long as no permanent study discontinuation criteria have been met. The management of specific AEs and laboratory parameters is described below.

For subjects who discontinue study drug but continue study participation and are on standard of care therapies, these toxicity management requirements do not apply (including alerts from the central lab) and any intolerance to standard of care therapies should be managed by the prescribing physician.

**Serious Infections:** Subjects should be closely monitored for the development of signs and symptoms of infection during and after treatment with study drug. Study drug should be interrupted if a subject develops a serious infection or an opportunistic infection. A subject who develops a new infection during treatment with study drug should undergo prompt diagnostic testing appropriate for an immunocompromised subject. As appropriate, antimicrobial therapy should be initiated, and the subject should be closely monitored. Study drug may be restarted once the infection has been successfully treated or resolved. Subjects who develop active TB or experience Hepatitis B reactivation must be discontinued from study drug. For subjects who develop TB during the study, the supplemental eCRF should be completed.

**COVID-19:** Interrupt study drug in subjects with a confirmed diagnosis of COVID-19. Consider interrupting study drug in subjects with signs and/or symptoms and suspicion of COVID-19. The COVID-19 eCRF must be completed. If a subject has a confirmed or suspected SARS-CoV-2 infection and study drug was interrupted, the investigator should contact the AbbVie TA MD before reintroducing study drug.

**Malignancy:** Subjects who develop malignancy other than NMSC or carcinoma in situ of the cervix must be discontinued from study drug. Information including histopathological results should be queried for the confirmation of the diagnosis. The supplemental eCRF should be completed.

**ECG Abnormality:** Subjects must be discontinued from study drug for an ECG change considered clinically significant and with reasonable possibility of relationship to study drug OR a confirmed absolute QTcF value > 500 msec.

**Surgery:** Subjects who undergo emergency surgery should have study drug interrupted at the time of the surgery. After emergency surgery, reintroduction of study drug is allowed once the physician has examined the surgical site and determined that it has healed and there is no sign of infection.

**Management of Select Laboratory Abnormalities:** For any given laboratory abnormality, the Investigator should assess the subject, apply the standard of care for medical evaluation and treatment following any local guidelines. Specific toxicity management guidelines for abnormal laboratory values are described in [Table 2](#) and may require an appropriate supplemental eCRF be completed. All

---

abnormal laboratory tests that are considered clinically significant by the Investigator will be followed to a satisfactory resolution. If a repeat test is required per [Table 2](#), the repeat testing must occur as soon as possible. Subjects who meet any of the criteria for ALT and/or AST listed in [Table 2](#) should be evaluated for an alternative etiology and managed as medically appropriate per local guidelines. The investigator should contact the AbbVie TA MD to discuss the management of a subject when an alternative etiology has been determined. The alternative etiology should be documented appropriately in the eCRF; study drug should be discontinued if no alternative etiology can be found.

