### 3.4 Additional Efficacy Endpoints

---

- Change from Baseline in modified Baron score over time (at visits with endoscopy)
- Proportion of subjects with achievement of SFS = 0, RBS = 0, and Mayo endoscopic subscore = 0 over time (at visits with endoscopy)
- Time to clinical response per Partial Adapted Mayo score
- Proportion of subjects with endoscopic improvement over time (at visits with endoscopy)
- Proportion of subjects with clinical remission per Adapted Mayo score over time (at visits with endoscopy)
- Proportion of subjects with clinical response per Adapted Mayo score over time (at visits with endoscopy)
- Proportion of subjects with clinical response per Partial Adapted Mayo score over time
- Proportion of subjects with achievement of clinical remission per Adapted Mayo score over time among subjects who were taking corticosteroids at Baseline and subsequently discontinued corticosteroids for  $\geq$  90 days prior to the respective visit.
- Proportion of subjects with discontinuation of corticosteroid use for subjects taking corticosteroids at Baseline at all visits over time
- Proportion of subjects with endoscopic remission over time (at visits with endoscopy)
- Proportion of subjects with clinical remission per Full Mayo score over time in subjects with a Full Mayo score of 6 to 12 at Baseline (at visits with endoscopy)
- Proportion of subjects with clinical response per Full Mayo score over time in subjects with a Full Mayo score of 6 to 12 at Baseline (at visits with endoscopy)
- Proportion of subjects with SFS  $\leq$  1 over time
- Proportion of subjects with RBS = 0 over time
- Change from Baseline in RBS over time
- Change from Baseline in SFS over time
- Change from Baseline in fecal calprotectin (FCP) over time
- Change from Baseline in high sensitivity C-reactive protein (hs-CRP) over time
- Change from Baseline in Inflammatory Bowel Disease Questionnaire (IBDQ) over time
- Proportion of subjects with UC-related Hospitalizations (yes/no) over time
- Proportion of subjects with UC-related surgery (yes/no) over time
- Proportion of subjects reporting no bowel urgency over time
- Change from Baseline in weekly abdominal pain score over time

- Proportion of subjects with achievement of  $\geq 30\%$  reduction from Baseline in weekly abdominal pain score over time
- Proportion of subjects with weekly abdominal pain score = 0 over time

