### Disease Activity

- ✓ 6. Diagnosis of UC for at least 3 months prior to Baseline. Appropriate documentation of biopsy results consistent with the diagnosis of UC in the assessment of the Investigator, must be available.
- ✓ 7. Subject meets the following disease activity criteria: Active UC with an Adapted Mayo score of 5 to 9 points and endoscopic subscore of 2 to 3 (confirmed by central review).
- ✓ 8. No current diagnosis of CD or inflammatory bowel disease-unclassified (IBD-U).
- ✓ 9. No extent of inflammatory disease limited to the rectum as assessed by screening endoscopy.
- ✓ 10. No currently known complications of UC such as:
  - fulminant colitis,
  - toxic megacolon,
  - previous colectomy (total or subtotal),
  - or any other manifestation that might require surgery while enrolled in the study
- ✓ 11. Subjects must not have an ostomy or ileoanal pouch.

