## 5.5 Withdrawal of Subjects and Discontinuation of Study Drug or from Study Participation

---

A subject may voluntarily withdraw or be withdrawn from study participation, or be discontinued from study drug, at any time for reasons including, but not limited to, the following:

- Disease progression or lack of response to treatment.

- Clinically significant abnormal laboratory results or AEs, which rule out continuation of the study drug, as determined by the investigator or the AbbVie TA MD.
- The investigator believes it is in the best interest of the subject.
- The subject requests withdrawal from the study. This includes if a subject would like to discontinue after completion of the Week 52 visit.
- Eligibility criteria violation was noted after the subject started study drug and continuation of the study drug would place the subject at risk.
- Introduction of prohibited medications or dosages and continuation of the study drug would place the subject at risk.
- The subject becomes pregnant while on study drug.
- Subject has a malignancy, except for localized non-melanoma skin cancer. Discontinuation for carcinoma in situ of the cervix is at the discretion of the Investigator.
- Subject is significantly noncompliant with study procedures, which would put the subject at risk for continued participation in the trial.

Subjects who complete the induction period and do not achieve clinical response per Partial Adapted Mayo score at Week 12 will be discontinued.

For subjects to be considered lost to follow-up, reasonable attempts must be made to obtain information on the subject's final status. At a minimum, 2 telephone calls must be made and 1 certified letter must be sent and documented in the subject's source documentation.

AbbVie may terminate this study prematurely, either in its entirety or at any site. The investigator may also stop the study at his/her site if he/she has safety concerns. If AbbVie terminates the study for safety reasons, AbbVie will promptly notify the investigator.

During states of emergency or pandemic situations, it may be necessary to employ mitigation strategies to enable the investigator to ensure subject safety and continuity of care. Acceptable mitigation strategies are identified and included in the Operations Manual in [Appendix F](#).

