8.0 Efficacy Analyses

8.1 General Considerations

UC-Related corticosteroids intercurrent events are defined as follows:

- subjects not on UC-related corticosteroids (systemic or locally acting corticosteroids for UC) at Baseline who initiated UC-related corticosteroids during the Induction Period;
- subjects on UC-related systemic corticosteroids at Baseline who had dosages increased to greater than the prednisone equivalent dose of corticosteroid at Baseline, or initiation of any rectal corticosteroids during the Induction Period regardless of rectal corticosteroid dose.

The time point of the UC-related corticosteroids intercurrent event is defined as the date when one of the scenarios above occurs for a subject. As such, subjects will be considered as "non-responder" for binary endpoints at or after the occurrence of the UC-related corticosteroids intercurrent event through the end of the Induction Period. For continuous endpoints, all measurements at or after the occurrence of the UC-related corticosteroids intercurrent event through the end of the Induction Period will not be used in the analysis.

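### SAP 8.1 has no rule for UC-related surgery, so diary scores recorded after a colectomy can count as symptomatic response

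*Protocol*

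**What the plan says.** **Analysis rules.** SAP 8.1 opens its only list of such events with "UC-Related corticosteroids intercurrent events are defined as follows". That list covers starting or increasing UC-related corticosteroids, and its effect ends with the induction period. Under SAP 8.2, NRI-C turns two things into non-response: a missing evaluation (unless due to COVID-19) and a corticosteroid event. The as-observed (AO) method uses every recorded value and drops subjects who have none. SAP 8.5 analyses maintenance endpoints with AO data only.

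**Surgery as data.** Operations Manual 2.1 captures UC-related surgery for the whole study. Protocol 3.4 reports it as an endpoint of its own, "Proportion of subjects with UC-related surgery (yes/no) over time", and SAP 3.3 repeats this. Neither document links it to response status.

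**Surgery and study conduct.** Protocol 6.2 interrupts drug at emergency surgery and then states "After emergency surgery, reintroduction of study drug is allowed once the physician has examined the surgical site and determined that it has healed", provided there is no infection. It also says "There are no time limits for study drug interruption as long as no permanent study discontinuation criteria have been met". Protocol 5.5 does not name colectomy; its wording is permissive ("A subject may voluntarily withdraw or be withdrawn from study participation, or be discontinued from study drug, at any time for reasons including") and its nearest listed reason is "Disease progression or lack of response to treatment". Colectomy, ostomy and pouch appear only as entry exclusions in 5.1, for example "Subjects must not have an ostomy or ileoanal pouch". Section 5.6 asks that subjects who stop drug early still attend all scheduled visits unless they withdraw consent.

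**The concern.** The SAP counts a subject who starts UC corticosteroids in induction as a non-responder, but has no such rule for a subject whose colon is removed for UC. The Partial Adapted Mayo score consists of two diary items, stool frequency (SFS) and rectal bleeding (RBS), and a day with no visible blood scores RBS 0. Once the bleeding bowel is gone, RBS can fall to 0 for a reason that is not drug benefit.

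The endpoints exposed are those built only on the diary: Partial Adapted Mayo response over time (a key secondary endpoint), time to that response, RBS = 0 and no bowel urgency. The same response at Week 12 is the gate into maintenance in protocol 4.1. In maintenance the exposure lasts 92 weeks, and neither a non-responder rule nor an intercurrent-event rule applies.

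**Working it through.** The plan gives no figure of its own on this point, so the check applies its definitions.

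**Inputs**
- Eligibility (protocol 5.1, criterion 7): Adapted Mayo 5 to 9 with endoscopy subscore 2 or 3.
- Partial Adapted Mayo response (protocol 3.3): fall of at least 1 point and at least 30%, plus an RBS fall of at least 1 or RBS of at most 1.
- Planned N: about 40; interim at about 30 (protocol 4.1 and 7.3).
- Simplification: whole-number subscores. Visit values are in fact three-day averages.

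**Step 1: eligible baselines.** With endoscopy at most 3, eligibility requires SFS + RBS of at least 2. That gives 13 pairs. Two, (2,0) and (3,0), have no bleeding, which leaves 11.

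**Step 2: set RBS to 0.** Fall = (SFS + RBS at baseline) − SFS afterwards; percentage = fall / (SFS + RBS at baseline). The RBS condition is always met.

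| Baseline (SFS, RBS) | Sum | SFS unchanged | SFS 3 afterwards |
|---|---|---|---|
| (0,2) | 2 | 2, 100%: yes | rise: no |
| (0,3) | 3 | 3, 100%: yes | 0: no |
| (1,1) | 2 | 1, 50%: yes | rise: no |
| (1,2) | 3 | 2, 67%: yes | 0: no |
| (1,3) | 4 | 3, 75%: yes | 1, 25%: no |
| (2,1) | 3 | 1, 33%: yes | 0: no |
| (2,2) | 4 | 2, 50%: yes | 1, 25%: no |
| (2,3) | 5 | 3, 60%: yes | 2, 40%: yes |
| (3,1) | 4 | 1, 25%: no | 1, 25%: no |
| (3,2) | 5 | 2, 40%: yes | 2, 40%: yes |
| (3,3) | 6 | 3, 50%: yes | 3, 50%: yes |
| **Total** | | **10 of 11** | **3 of 11** |

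**Step 3: effect per subject in induction.** 1/40 = 2.5 points; at the interim, 1/30 = 3.3 points.

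**Step 4: maintenance.** The documents give no denominator. If 10 to 20 subjects are observed at a visit, one subject adds 1/20 = 5 to 1/10 = 10 points. Illustration, with all counts assumed: 20 subjects, 8 true responders, 2 colectomies.
- Surgery scored as failure: 8/20 = 40%.
- Diary values counted as response: (8 + 2)/20 = 50%.
- Endoscopic endpoint, value missing under AO: 8/18 = 44%.

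With 1 or 3 colectomies, counting the diary values gives 9/20 = 45% or 11/20 = 55%, against 40%.

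**Step 5: which endpoints are protected.** If endoscopy cannot be evaluated at Week 8, NRI-C gives non-response on the primary endpoint, Adapted Mayo remission, Adapted Mayo response, Full Mayo remission and endoscopic remission. Of the five key secondary endpoints, only Partial Adapted Mayo response needs no endoscopy.

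**The case against.** **The 6.2 restart rule as the cause.** A reader might infer that 6.2 creates the problem by letting drug restart after colectomy. The documents do not support that. The paragraph concerns wound healing and infection, is permissive and does not name colectomy. The scoring gap is there without any restart, because 5.6 continues the visits. Withdrawal under 5.5 is possible and its list is open-ended, but no rule scores stopping drug as non-response.

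**Bias in the primary endpoint.** A reader might infer this too. Step 5 shows otherwise, as long as the Week 8 endoscopy is missing for a reason other than COVID-19.

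**The entry exclusions as evidence.** It is tempting to say that criteria 10 and 11 exist because Mayo items cannot be read after such surgery. Section 5.1 gives no reason, and entry criteria answer a different question from on-study rules.

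**Size.** Ten of 11 is the favourable end and needs stool frequency to be unchanged after colon surgery; with SFS 3 it is 3 of 11. The documents do not say how the diary items are scored with an ostomy. If the assessment is missing in induction, NRI-C already gives non-response, and UC corticosteroids started or increased in induction would trigger the existing rule. An induction effect also needs surgery, recovery and valid diary entries within 12 weeks.

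**Visibility.** UC-related surgery and serious adverse events are reported separately in a small open-label study, so a colectomy would be seen.

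These points narrow the concern to diary-only endpoints and give a range in place of a single count. They do not remove it: separate reporting does not correct the response rate, and in maintenance neither NRI-C nor the corticosteroid rule applies.

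**Conclusion.** The concern holds for the diary-only endpoints in both periods. As written, the rules use post-surgery diary values as observed, and a treatment failure can enter as a success. The direction favours the drug.

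The size is 2.5 points per affected subject at N = 40 in induction. In maintenance it is 5 to 10 points, on the assumption of 10 to 20 observed subjects. Whether a given subject is affected depends on stool frequency afterwards: 3 to 10 of the 11 eligible bleeding baselines would qualify if RBS falls to 0. The number of such surgeries is unknown, may be zero and is likely small.

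The primary endpoint and four of the five key secondary endpoints are largely protected at Week 8. In maintenance, a subject without an evaluable endoscopy leaves the denominator of the endoscopic endpoints, which also raises the rate. This should be corrected before database lock, but it does not threaten the primary conclusion.

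**What to change.** **SAP 8.1.** Define UC-related surgery (colectomy, or creation of an ostomy or pouch) as an intercurrent event in both periods. From the surgery date:
- the subject is a non-responder on all binary efficacy endpoints;
- the subject stays in the denominator in maintenance, as a stated exception to AO;
- later continuous efficacy values are not used, in line with the existing corticosteroid rule;
- no first response is counted in the time-to-response analysis.

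**Cost.** This is SAP wording. UC-related surgery is already collected for the whole study on the HCRU form; confirm that the form records the date, which Operations Manual 2.1 does not state. The response rate may be slightly lower. Dropping continuous values does not score failure (MMRM assumes missing at random, and AO means simply lose the subject), so report how many subjects are affected.

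**Protocol.** The SAP change does not alter the Week 12 gate or the conduct rules. Protocol 5.1 (criteria 10 and 11), 5.5 and 6.2 should be reconciled so that it is clear whether such surgery falls under the 6.2 surgery paragraph. No clinical rule is proposed here.

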		ALT or AST $> 8 \times$ ULN	
 
Interrupt study drug dosing and redraw lab with a new sample.
 
If value is confirmed, discontinue study drug and complete supplemental hepatic eCRF.
 

		ALT or AST $> 5 \times$ ULN	
 
Interrupt study drug dosing and redraw lab with a new sample.
 
If value is confirmed for <math>> 2</math> weeks of duration, discontinue study drug and complete supplemental hepatic eCRF.
 

		ALT or AST $> 3 \times$ ULN	
 
Interrupt study drug dosing and redraw lab with a new sample.
 
If value is confirmed and patient has appearance of fatigue, nausea, vomiting, right upper quadrant pain or tenderness, fever, rash, and/or eosinophilia (<math>> 5\%</math>) discontinue study drug and complete supplemental hepatic eCRF.
 
If value is confirmed and total bilirubin <math>> 2 \times</math> ULN or international normalized ratio (INR) <math>> 1.5</math>, discontinue study drug and complete supplemental hepatic eCRF.
 

	Serum Creatinine	$> 1.5 \times$ the baseline value and $>$ ULN	
 
Interrupt study drug dosing and redraw lab with a new sample.
 
If value is confirmed, continue to withhold study drug until value returns to normal reference range or baseline value.
 

		$\geq 2$ mg/dL	
 
Interrupt study drug dosing and redraw lab with a new sample.
 
If value is confirmed, continue to withhold study drug until value returns to normal reference range or baseline value.
 

	ALT or AST	$> 5 \times$ ULN	
 
Interrupt study drug dosing and redraw lab with a new sample.
 
If value is confirmed, send HBV DNA by PCR.
 
If HBV DNA by PCR is positive, discontinue study drug and complete supplemental hepatic eCRF.
 

Subjects who are HBc Ab+ and HBV DNA negative at Screening			

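### Protocol section 6.2 gives two different outcomes for some raised ALT/AST results when no alternative cause is found

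*Protocol*

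**What the plan says.** Two parts of Protocol section 6.2 deal with the same laboratory results.

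The paragraph on select laboratory abnormalities opens its liver rule with "Subjects who meet any of the criteria for ALT and/or AST listed in" Table 2. Those subjects are to be evaluated for another cause. If one is found: "The investigator should contact the AbbVie TA MD to discuss the management of a subject when an alternative etiology has been determined". If none is found: "study drug should be discontinued if no alternative etiology can be found". The paragraph does not repeat any condition on confirmation, duration, symptoms, bilirubin or INR.

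Every ALT/AST row of Table 2 starts with interruption and a redraw. The discontinuation conditions then differ by level:

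- > 8 x ULN: "If value is confirmed, discontinue study drug and complete supplemental hepatic eCRF".
- > 5 x ULN: the value must be confirmed for > 2 "weeks of duration, discontinue study drug and complete supplemental hepatic eCRF".
- > 3 x ULN, first branch: "If value is confirmed and patient has appearance of fatigue, nausea, vomiting, right upper quadrant pain or tenderness, fever, rash", or eosinophilia.
- > 3 x ULN, second branch: "If value is confirmed and total bilirubin" is > 2 x ULN or INR is > 1.5.

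None of these rows refers to cause. A separate > 5 x ULN row, for subjects positive for hepatitis B core antibody and negative for HBV DNA at Screening, ties discontinuation to a positive HBV DNA result and is not needed for the comparison below.

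**The concern.** Both passages are current instructions in one section, and no sentence ranks them or says how they combine. A site that works from the table and a site that works from the paragraph can therefore reach different decisions on the same laboratory course.

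The difference is not just one of labels. Section 6.2 sets no time limit on interruption as long as no permanent discontinuation criterion has been met, so a site has to know which passage defines those criteria.

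Inconsistent handling of subjects comes first. It then carries into the analysis: SAP section 5.0 counts premature discontinuations of study drug by reason, and SAP section 9.2.2 counts adverse events leading to discontinuation. One laboratory course could appear as a discontinuation at one site and as an interruption at another.

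**Working it through.** The plan gives no figure to reproduce. The check sets the two passages side by side. Here, features means the listed symptoms, eosinophilia, bilirubin > 2 x ULN or INR > 1.5.

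| Case | Text of 6.2 | Table 2 | Result |
|---|---|---|---|
| 1. Confirmed > 3 to 5 x ULN, no features, no cause found | Discontinue | Interrupt and redraw, then silent | Differ |
| 2. > 5 to 8 x ULN, not yet confirmed for > 2 weeks, no features, no cause found | Discontinue | Interrupt and redraw; discontinuation condition not yet met | Differ |
| 3. A table discontinuation condition is met (such as confirmed > 8 x ULN), no cause found | Discontinue | Discontinue | Agree |
| 4. As case 1 or 2, but a cause is found | Discuss management | Interrupt and redraw, then silent | Neither requires discontinuation |
| 5. A table discontinuation condition is met, a cause is found | Discuss management | Discontinue | Unclear |

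**How far this depends on the word criteria.** If it means the thresholds in the table's Value column, cases 1 and 2 differ. If it means the complete discontinuation conditions, cases 1 and 2 drop out. On that narrower reading, however, the table already discontinues every subject the text reaches. The text's stopping clause would then add nothing unless a known cause relaxes a table row, which is the open question in case 5. Neither reading removes the need for clarification.

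**What other rows of Table 2 show.** Where cause is meant to matter, the table can say so: the hemoglobin rows make interruption depend on whether another etiology is identified. Where drug is to be withheld after confirmation, the table can say that too: the ALC, white cell, platelet and creatinine rows, and the ANC < 1000 row, withhold until the value is back in the normal range or at baseline. The > 3 x and > 5 x ULN rows do neither. After a confirmed value that meets no discontinuation condition, they give no next step.

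**Size per subject.** Taking the planned enrolment of about 40 as the denominator, one subject classified differently changes a discontinuation percentage by 1/40 = 2.5 percentage points. The documents do not say how many such results to expect.

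**The case against.** The best defence is that the passages are cumulative: interrupt, redraw, look for a cause, and discontinue if either the paragraph or a table row requires it. Table 2 never says that discontinuation is limited to its listed conditions, and in case 1 it is silent rather than opposed. In case 2 drug is already interrupted, so part of the difference is timing. Subjects are not dosed through an unresolved elevation, section 5.5 lets the investigator or the sponsor's medical director stop drug for clinically significant laboratory results, and entry requires ALT and AST of no more than 2 x ULN.

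These facts stand and limit the consequences. They do not settle the wording. No sentence says that the rules are cumulative. If they are, then whenever no cause is found the table's duration, symptom, bilirubin and INR conditions no longer decide anything, because the paragraph already discontinues at > 3 x ULN.

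A reader might infer three stronger points, none of which the documents support:

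- That text and table conflict for every value > 3 x ULN without symptoms, bilirubin or INR findings. They do not: case 3 agrees (including > 5 x ULN for > 2 weeks with no cause), and in case 4 neither requires discontinuation.
- That confirmed > 8 x ULN with a known cause is a direct contradiction. The text asks only for a discussion of management; it neither waives the table row nor permits continued dosing. A site could discontinue and still hold the discussion. This is an ambiguity.
- That counts of hepatic adverse events of special interest would change. The criterion in Protocol section 6.1 covers discontinuation or interruption due to a hepatic event, and every ALT/AST row begins with interruption. SAP section 9.2.6 identifies hepatic events by MedDRA queries, not by action taken with study drug.

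**Conclusion.** The inconsistency is real and narrow. It applies when no alternative cause is found and no table discontinuation condition is met: confirmed > 3 to 5 x ULN without the listed features, or > 5 to 8 x ULN without them and not yet confirmed for > 2 weeks. This assumes that criteria refers to the Value-column thresholds, which is the plainer reading because the text speaks of meeting any of them. Separately, the effect of a known cause on the table's discontinuation rows is left unstated.

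The consequence is inconsistent handling of subjects and possibly inconsistent counts of study drug discontinuation and of adverse events leading to it. The 2.5 points per subject assumes a denominator of 40. No effect on the primary endpoint or on adverse events of special interest is shown. The point deserves correction because following the plan as written can give two outcomes for one result, even if few subjects are affected.

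**What to change.** Reconcile the liver paragraph of Protocol section 6.2 with the ALT/AST rows of Table 2. The revised wording should settle four things:

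1. whether the etiology rule adds to the graded rows, replaces them, or applies only once a row's conditions are met;
2. whether criteria means the threshold values or the complete discontinuation conditions;
3. whether a known cause modifies the rows that call for discontinuation;
4. what follows interruption when a value is confirmed but no discontinuation row is met.

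The sponsor's medical team decides the content of each rule; none is proposed here. The cost is a wording change within one section, with the ethics committee review that Protocol section 8.1 requires for any amendment. No assessment, data field or SAP analysis needs to change.
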